8.2.2. Exclusion criteria

Patients meeting any of the following criteria will not be included in the study:

- Patients with prior BRAF- or MEK-inhibitor therapy
- Patients with ECOG performance status ≥ 2 (at the time of randomization for patients from COLUMBUS, during the baseline period for patients in Flatiron EHR)
- Patients with a history of leptomeningeal metastases including brain, spinal cord, or nervous system metastases (based on brain MRI or CT scan with contrast-enhanced brain MRI as the preferred assessment in COLUMBUS and based on the following

diagnostic codes in Flatiron EHR: ICD-9-CM: 198.3, 198.4 or ICD-10-CM: C79.31, C79.32, C79.40, C79.49) prior to index

For RWD patients, concurrent enrollment in a clinical trial.

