- 1. Pooling of data for encorafenib + binimetinib patients across the phase 3 COLUMBUS trial and the Flatiron Health real-world database: The pooling of data for encorafenib + binimetinib patients across these two sources is justified by the results of study C4221035, which showed, that after harmonizing key patient selection criteria, adjusting for differences in baseline characteristics, and imputing missing data on baseline characteristics, OS for metastatic BRAFV600-mutant melanoma patients was similar across the COLUMBUS trial and real-world practice data from the Flatiron Health database (HR = 1.03, 95% CI: 0.53, 1.54; p=0.90). Given this empirical consistency in OS outcomes, pooling patients across these settings can be justified and allows for a larger sample size for assessment of comparative effectiveness of encorafenib + binimetinib versus other targeted therapies.
- 2. Application of key patient selection criteria consistent with the COLUMBUS trial for all treatment groups: To ensure included patient populations are comparable across settings, key patient selection criteria applied from the COLUMBUS trial will also be applied to all treatment groups drawn from the Flatiron real-world database. These include the following: age ≥18 years at initiation of targeted therapy, metastatic BRAF V600E/K mutated melanoma without central nervous system metastases, untreated or with prior first-line immunotherapy, and ECOG performance status of 0 or 1.
- Imputation of missing data on baseline characteristics: To allow for more
 comprehensive adjustment for confounding due to differences in baseline characteristics
 between treatment groups, multiple imputation will be conducted to account for missing
 data in baseline characteristics.

The approach outlined here largely follows the approach described in *Protocol #C4221035*, with minor updates to the selection criteria, adjustment factors and statistical methods following discussions with a clinical expert in melanoma and further review of the clinical trial and real-world data.

Classification of Change as Substantial and Non-Substantial and Rationale

This is a Substantial Protocol Amendment for the reasons described above.

NON-INTERVENTIONAL (NI) STUDY PROTOCOL

Study information

Title	OCEANMIST - Comparative effectiveness of different targeted therapies for BRAF-mutated unresectable/metastatic melanoma in the United States	
Protocol number	C4221028	
Protocol version identifier	2.0	
Date	19 JUL 2023	

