8.9. Strengths and limitations of the research methods

The strengths of this study include:

- Key inclusion criteria with respect to diagnosis, disease stage, age, BRAFV600 mutation and ECOG status in the COLUMBUS trial will be applied to the Flatiron RWD to the extent possible to obtain a comparable group of patients across both settings
- Adjustment will be made for multiple baseline characteristics to mitigate bias due to potential differences in these characteristics across the treatment groups
- Concerns about differences in outcome assessment across trial and RWD settings are
 mitigated for OS given the availability of a real-world mortality endpoint in the Flatiron
 RWD that has high sensitivity, specificity, positive predictive values, negative predictive
 values and agreement when compared against the National Death Index (NDI), the goldstandard source for mortality data in the US.¹⁷

The limitations of this study include the following:

- Application of the COLUMBUS trial inclusion criterion requiring at least 1 measurable lesion based on Response Evaluation Criteria in Solid Tumors (RECIST) version 1.1 criteria will not be implemented due to absence in Flatiron EHR of systematic radiographic imaging to assess tumor response as required by RECIST.
- While adjustment will be made for available baseline characteristics across treatment
 groups, differences due to factors that were not adjusted for may still contribute to
 observed differences in OS between settings. For instance, data on number and sites of
 metastases, while systematically collected in the COLUMBUS trial, can only be derived
 based on ICD codes in Flatiron EHR. Based on clinical input, data on number and sites
 of metastases will very likely be underestimated in the Flatiron EHR, and not
 comparable to the corresponding data from COLUMBUS, precluding adjustment for
 these variables.

- The analysis conducted here is analogous to an 'intent-to-treat' perspective, and therefore will not account for potential differences in adherence and post-baseline treatments between trial and real-world settings.
- The COLUMBUS trial was a multi-national trial that recruited patients from 160+ sites in 28 countries, and therefore covers a broader range of geographies than the US-based Flatiron RWD; differences in background care across geographies and care settings may contribute to differences in outcomes between the CTD and RWD.

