2.1 STUDY DESIGN

This is a retrospective cohort study comparing OS outcomes between patients with BRAFV600-mutant metastatic melanoma initiating encorafenib plus binimetinib (ENCO+BINI) versus dabrafenib plus trametinib (DAB+TRAM) or vemurafenib plus cobimetinib (VEM+COBI). Comparisons will be adjusted for differences in baseline characteristics across treatment groups, and account for missing data on adjustment factors. PFS will also be investigated as an exploratory endpoint, subject to comparability of PFS outcome assessment between clinical trial and real-world settings.

Study population

The study population will consist of patients with BRAFV600-mutant metastatic melanoma initiating treatment with ENCO+BINI, DAB+TRAM or VEM+COBI. Data for ENCO+BINI will be pooled across COLUMBUS and Flatiron data, while data for DAB+TRAM and VEM+COBI will be from Flatiron data. The number of patients eligible for the study will be determined in accordance with the sample selection conducted per the inclusion and exclusion criteria described in Section 4.

Data source

COLUMBUS trial

COLUMBUS was a two-part, multicenter, randomized, open-label, Phase 3 clinical trial. Part 1 of the trial investigated the effectiveness and safety of three treatment regimens in patients with locally advanced unresectable or metastatic BRAFV600-mutant metastatic melanoma who were treatment naïve or whose cancer had progressed after 1L IO. In Part 1 of the trial, patients were randomized to one of three treatment arms: 1) 450mg once daily encorafenib and 45mg twice daily binimetinib (n=192), 2) 960mg twice daily vemurafenib (n=191) and 3) 300mg once daily encorafenib (n=194). Randomization was stratified by AJCC disease stage (IIIB, IIIC, IVM1a, IVM1b, or IVM1c), ECOG performance status (0, 1), and BRAFV600 mutation profile (V600E, V600K). Progression-free survival was the primary endpoint in the trial, while OS was one of the secondary endpoints. Patients were enrolled in Part 1 of the trial between 30 December 2013 through 10 April 2015.

The ENCO+BINI arm of Part 1 of the trial will be used in this study (database lock date: 15 September 2020) and combined with the ENCO+BINI cohort from Flatiron EHR identified below. Part 2 of the trial compared encorafenib 300mg once daily plus binimetinib 45mg twice daily versus encorafenib 300mg once daily alone and will not be considered.

Flatiron Health EHR

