Key inclusion criteria from the COLUMBUS trial will be applied to the Flatiron RWD population to align the populations to the extent possible between the CTD and RWD sources. The sample of patients from the Flatiron Health EHR data for this study will be identified using the following additional criteria applied to the custom data cut received from Flatiron:

- At least 18 years of age at the index date
- Confirmed BRAF V600E or V600K activating mutation reported in the data based on laboratory or genetic analysis results
- Treatment-naive or had previous 1L IO at index date in the therapeutic setting, based on review of medication orders or administration prior to the index date.
- ECOG status of 0 or 1 at the index date

The following criteria will be additionally used to identify patients receiving each of the treatments of interest:

- ENCO+BINI treatment group: At least 1 order or administration of ENCO+BINI treatment after the diagnosis of metastatic melanoma and after 27 June 2018 (FDA approval date for ENCO+BINI for use in patients with metastatic melanoma).
- DAB+TRAM treatment group: At least 1 order or administration of DAB+TRAM treatment after the diagnosis of metastatic melanoma and after 09 January 2014 (FDA approval date for DAB+TRAM for use in patients with metastatic melanoma).
- VEM+COBI treatment group: At least 1 order or administration of VEM+COBI treatment after the diagnosis of metastatic melanoma and after 10 November

2015 (FDA approval date for VEM+COBI for use in patients with metastatic melanoma).

The index date in each treatment group will be the date of treatment initiation.

Exclusion criteria

Patients meeting any of the following criteria will not be included in the study:

- Patients with prior BRAF- or MEK-inhibitor therapy
- Patients with ECOG performance status ≥ 2 (at the time of randomization for patients from COLUMBUS, during the baseline period for patients in Flatiron EHR)
- Patients with a history of leptomeningeal metastases including brain, spinal cord, or nervous system metastases (based on brain MRI or CT scan with contrastenhanced brain MRI as the preferred assessment in COLUMBUS, and based on the following diagnostic codes in Flatiron EHR: ICD-9-CM: 198.3, 198.4 or ICD-10-CM: C79.31, C79.32, C79.40, C79.49) prior to index
- For RWD patients, concurrent enrollment in a clinical trial.

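### CNS metastases are excluded by brain imaging in COLUMBUS but by pre-index ICD codes in Flatiron, so missed CNS disease could fall mainly on the comparators and could bias OS towards ENCO+BINI

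*Protocol*

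**What the plan says.** The Protocol's summary of changes (key element 2) lists "metastatic BRAF V600E/K mutated melanoma without central nervous system metastases" among the COLUMBUS criteria to be applied to all Flatiron groups. Protocol section 4 and SAP section 1 likewise list history of brain metastasis among the criteria carried over.

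Protocol 8.2.2 applies the restriction differently by source:

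- **COLUMBUS:** "based on brain MRI or CT scan with contrast-enhanced brain MRI as the preferred assessment in COLUMBUS".
- **Flatiron:** "diagnostic codes in Flatiron EHR: ICD-9-CM: 198.3, 198.4 or ICD-10-CM: C79.31, C79.32, C79.40, C79.49) prior to index". No brain imaging is required. SAP 4.1 has the same rule, ending "C79.31, C79.32, C79.40, C79.49) prior to index".

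Protocol 8.9 says of ICD-derived data that the number and sites of "metastases will very likely be underestimated in the Flatiron EHR" and are not comparable with COLUMBUS, "precluding adjustment for" these variables. It does not mention the CNS exclusion, which depends on the same kind of code.

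The sources are not spread evenly over the groups. SAP 2.1 states: "Data for ENCO+BINI will be pooled across COLUMBUS and Flatiron data, while data for DAB+TRAM and VEM+COBI will be from Flatiron data". The COLUMBUS ENCO+BINI arm has 192 patients (Protocol 8.4). The Flatiron ENCO+BINI cohort has no stated size; the summary of changes says only that it was too small for adjusted analysis.

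**The concern.** The protocol treats ICD codes as too incomplete to supply a metastasis covariate, yet relies on them as a hard eligibility filter for one metastatic site. If the codes miss CNS disease, affected patients stay in the Flatiron cohorts. Those cohorts are the whole of both comparators but only part of ENCO+BINI. If CNS disease worsens survival, comparator OS is depressed and the primary hazard ratio moves towards ENCO+BINI with no treatment difference.

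The date limit adds to this. Protocol 8.7.1 defines a three-month Flatiron baseline window that includes the index date, and the ECOG exclusion uses the baseline period. The CNS codes alone are limited to those before index. Read literally, a patient whose CNS lesion is first coded on the day treatment starts is kept.

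The planned output would not show the problem:

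- The lung, liver and other-site code lists in Table 1 contain none of the six CNS codes.
- The optional sensitivity analyses in SAP 7.1 concern extra covariates and the time frame of treatment initiation, not CNS ascertainment or data source.

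**Working it through.** The plan gives no sample size, event count or power, so it has no figure of its own to reproduce. The steps below show how the imbalance arises and how large it could be.

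**Inputs.** From the documents: 192 COLUMBUS ENCO+BINI patients, and comparators wholly from Flatiron. Assumed: q, the share of Flatiron patients with undetected CNS disease; h, their mortality hazard ratio; m, the number of Flatiron ENCO+BINI patients; exponential OS with a stated median; and the censoring pattern.

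**Step 1: dilution.** The Flatiron share of pooled ENCO+BINI is s = m/(192 + m):

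- m = 20: 20/212 = 9%
- m = 50: 50/242 = 21%
- m = 100: 100/292 = 34%
- m = 192: 192/384 = 50%

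Undetected CNS prevalence is q in each comparator and s·q in ENCO+BINI, taking it as zero in COLUMBUS.

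**Step 2: model.** With λ = ln 2/median, survival at prevalence p is (1 − p)·exp(−λt) + p·exp(−hλt). Set p = q for a comparator and p = s·q for ENCO+BINI, with no treatment effect. The large-sample Cox hazard ratio solves the partial-likelihood score equation.

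Hand check at time zero: the ratio is [1 + s·q(h − 1)]/[1 + q(h − 1)]. For s = 0.25, q = 10%, h = 2 it is 1.025/1.10 = 0.93. The Cox value averages over follow-up as high-risk patients die, and is nearer 1.

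**Step 3: results with median 24 months, censoring uniform over 3-60 months, s = 25%.**

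| q | h | Unadjusted HR, ENCO+BINI vs comparator |
|---|---|---|
| 5% | 2 | 0.975 |
| 10% | 2 | 0.950 |
| 10% | 3 | 0.927 |
| 15% | 2 | 0.926 |
| 15% | 3 | 0.893 |

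Appendix Table 3 uses ENCO+BINI as the reference, so these would appear there as reciprocals: 1/0.975 = 1.03 to 1/0.893 = 1.12.

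**Step 4: wider grid, median 30 months, administrative censoring at 60 months, m = 20 to 192.**

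- q = 5%, h = 2: 0.97 to 0.98
- q = 10%, h = 2: 0.95 to 0.97
- q = 20%, h = 2: 0.89 to 0.94
- q = 30%, h = 3: 0.78 to 0.87

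Over the whole grid (q 5-30%, h 1.5-3) the range is 0.78 to 0.99, always below 1.

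**Step 5: does study C4221035 rule this out?** It compared COLUMBUS with Flatiron and is reported as HR 1.03 (0.53 to 1.54) in SAP section 2. The log-scale standard error is ln(1.54/0.53)/3.92 = 0.272. The largest shift in Step 3 is |ln 0.893| = 0.113, or 0.113/0.272 = 0.42 standard errors. In that study the contrast would be undiluted. Even so, the time-zero ratio for q = 15%, h = 3 is 1/1.30 = 0.77 (1.30 in the other direction), and both values lie inside the interval. The other figure printed for that study, 0.94 (0.43 to 1.45) in Protocol section 6, is no more precise.

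**Step 6: a tempting check that misleads.** One could drop Flatiron patients with a CNS code soon after index and start the OS clock at a landmark. The plan has no matching code rule for COLUMBUS, so true early CNS progression would be removed from Flatiron only. Suppose there is no treatment effect and no baseline misclassification, and 3-5% of every group develop CNS disease before the landmark, with h = 2-3. After exclusion the prevalence is 0 in the comparators and 0.75 × 3-5% in ENCO+BINI. Under the Step 3 settings the hazard ratio is then 1.02 to 1.04. That artefact is about as large as the low-end bias it was meant to test.

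**The case against.** Five points can be made for the plan.

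- **It is partly disclosed.** 8.2.2 sets the two methods side by side, 8.2.1.2 claims alignment only as far as possible, and 8.9 already names ICD-derived metastatic sites as a source of residual differences. This stands. What is missing is the link from that limitation to the CNS exclusion.
- **The sensitivity of CNS codes is unknown.** 8.9 speaks of number and sites of metastases in general. This stands: neither q nor h can be taken from the documents, and low values give a small bias.
- **The model adjusts for ECOG and LDH.** A reader might infer that no listed covariate could correct the bias. The documents do not support that. If missed CNS disease goes with worse ECOG or raised LDH, adjustment absorbs some of it, and the figures above are unadjusted. How much is unknown, and section 4 reports 40-60% missing data on such characteristics in the original cohort.
- **Flatiron ENCO+BINI patients are filtered by the same codes.** True; this dilutes the imbalance and is already in the calculation.
- **C4221035 found similar OS in the two sources.** It is the only empirical evidence offered, but Step 5 shows it is too imprecise to exclude a bias of this size.

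The documents also do not give the timing or completeness of COLUMBUS brain imaging, so zero undetected CNS disease there is a simplification. Reading the code rule as strictly before index is the literal reading; it may be only loose wording.

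**Conclusion.** The unequal ascertainment is established by the documents, as is its uneven spread over the treatment groups. It could bias OS towards ENCO+BINI, provided that the codes miss some CNS disease and that such disease shortens survival. Under the narrower assumptions the unadjusted hazard ratio with no true effect is about 0.89-0.98; under the wider grid it is 0.78-0.99. These are illustrations, not estimates.

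A reader might infer that the primary result is biased in favour of ENCO+BINI. The documents do not support that. They give no sensitivity for CNS codes, no Flatiron ENCO+BINI count and no mortality effect of missed CNS disease. The trial and real-world sources also differ in other ways, so the net direction of bias in the adjusted hazard ratio is not known. What can be said is that the plan has no analysis able to show whether this component matters, and that its description of all groups as free of CNS metastases is stronger than the Flatiron rule supports.

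**What to change.** 1. **Date rule.** In Protocol 8.2.2 and SAP 4.1, count Flatiron CNS codes dated on or before the index date, in line with the baseline window in 8.7.1. Cost: a wording change and the loss of a few Flatiron patients.
2. **Sensitivity analyses.** Commit to comparing Flatiron ENCO+BINI with the Flatiron comparators, where CNS ascertainment is the same. It will be imprecise because that cohort is small, so read it for direction and width rather than significance. Add a simple quantitative bias analysis of the primary contrast over a stated range of undetected CNS prevalence and mortality hazard ratio. Do not use the landmark exclusion in Step 6.
3. **Description.** Tabulate Flatiron patients with a first CNS code 0-30, 31-60 and 61-90 days after index, by treatment group. With the new date rule, a day-0 code becomes an exclusion and should be counted as such. Use the table descriptively only, since later codes mix missed and new disease.
4. **Limitation.** In Protocol 8.9, state that the CNS exclusion is code-based in Flatiron, and qualify the no-CNS-metastases comparability claim wherever it is made.

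All of this uses data already held. No item recovers lesions that were never imaged or coded; the bias analysis is the only one that addresses them.

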8.3. Variables

Table 1 provides a summary of exposure, outcome, and patient baseline characteristics that will be evaluated within the study.

Table 1. Key exposures, outcomes, and patient baseline characteristics

Variable	Role	Data source(s)	Operational definition/categories
Treatment group (ENCO+BINI, DAB+TRAM, VEM+COBI)	Exposure	COLUMBUS trial data; Flatiron EHR	Indicates whether patients initiated ENCO+BINI, DAB+TRAM or VEM+COBI treatment
os	Primary Outcome	COLUMBUS trial data, Flatiron	In the COLUMBUS trial data, defined as the time from the date of randomization to the date of death due to any cause; if death is not observed, patients will be censored at the date of last contact or the data analysis cut-off date (e.g., 15 September 2020), whichever occurs first
	Timaly outcome		In Flatiron EHR, will be defined as the time from the index date to the date of death; patients without a date of death will be censored at their last known activity date (e.g., the last clinical note date) or the end of the follow-up period, whichever occurs first
	COLUMBUS	In the COLUMBUS trial data, defined as the time from the date of randomization to the date of the first documented disease progression or death due to any cause, whichever occurred first; if a patient did not have an event at the analysis cut-off date, PFS will be censored at the date of the last adequate tumour assessment	
PFS	Exploratory Outcome	trial data, Flatiron her	In Flatiron EHR, will be defined as the time from the index date to either the date of first disease progression event or death in the absence of progression; patients without disease progression or death will be censored at the last date the patient could have been assessed for progression (e.g., the last clinical note date) or the data analysis cut-off date (e.g., 30 September 2021), whichever occurs first
Age at baseline (years)	Baseline Characteristic / Potential Confounder	COLUMBUS trial data Flatiron EHR	Patient age; defined at the time of study randomization for COLUMBUS trial data and at the time of treatment initiation for Flatiron EHR
Sex	Baseline Characteristic / Potential Confounder	COLUMBUS trial data; Flatiron EHR	Male, Female, Intersex, or Unknown/Missing

Race	Baseline Characteristic / Potential Confounder	COLUMBUS trial data; Flatiron EHR	Asian, Black, White, Other/Multi-Race, or Unknown/Missing
Body mass index (BMI) at index	Baseline Characteristic / Potential Confounder	COLUMBUS trial data; Flatiron EHR	Defined as weight (in kg) divided by squared height (in m²)
ECOG at index	Baseline Characteristic / Potential Confounder	COLUMBUS trial data; Flatiron EHR	0, 1, Unknown/Missing; defined during the baseline period of both the COLUMBUS trial data and Flatiron EHR
BRAF mutation status	Baseline Characteristic / Potential Confounder	COLUMBUS trial data; Flatiron EHR	V600E, V600K, Unknown/Missing
AJCC disease stage at initial melanoma diagnosis	Baseline Characteristic / Potential Confounder	COLUMBUS trial data; Flatiron EHR	0, I, II, III, IV, or Unknown/Missing; defined at initial melanoma diagnosis for COLUMBUS trial data and Flatiron EHR
AJCC disease stage at treatment initiation	Baseline Characteristic	COLUMBUS trial data	IIIB, IIIC, IVM1a, IVM1b, or IVM1c; defined at treatment initiation in the COLUMBUS trial data. Not available in the Flatiron EHR
Lactate dehydrogenase (LDH) at index	Baseline Characteristic / Potential Confounder	COLUMBUS trial data; Flatiron EHR	Evaluated in units per liter (U/L) and defined at trial baseline in COLUMBUS trial and during the baseline period in Flatiron EHR
Time from initial melanoma diagnosis to metastatic disease	Baseline Characteristic / Potential Confounder	COLUMBUS trial data; Flatiron EHR	Duration (in months) from melanoma diagnosis to the development of metastatic disease
Time from metastatic melanoma diagnosis to treatment initiation	Baseline Characteristic / Potential Confounder	COLUMBUS trial data; Flatiron EHR	Duration (in months) from metastatic melanoma diagnosis to the initiation of treatment
Year of treatment initiation	Baseline Characteristic	COLUMBUS trial data; Flatiron EHR	Calendar year when treatment was initiated
Region	Baseline Characteristic	COLUMBUS trial data; Flatiron EHR	Europe, North America, Australia, Other, or Missing
Treatment experience in the therapeutic setting	Baseline Characteristic / Potential Confounder	COLUMBUS trial data; Flatiron EHR	Indicates whether patients received targeted therapy as first-line treatment (e.g., Treatment naïve) or as second- line treatment after a prior line of immunotherapy treatment (e.g., Prior 1L IO therapy)
Prior systemic therapies in the adjuvant setting	Baseline Characteristic /Potential Confounder	COLUMBUS trial data; Flatiron EHR	Indicates whether patients previously received systemic therapy (e.g., prior surgery, radiotherapy, immunotherapy, or chemotherapy) before initiating treatment
Prior surgery in the adjuvant setting	Baseline Characteristic / Potential Confounder	COLUMBUS trial data; Flatiron EHR	Indicates whether patients previously used surgery to reduce/remove tumors as a form of treatment
Prior radiotherapy in the adjuvant setting	Baseline Characteristic / Potential Confounder	COLUMBUS trial data; Flatiron EHR	Indicates whether patients underwent radiotherapy among those receiving prior systemic therapy

Prior IO or chemotherapy in the adjuvant setting	Baseline Characteristic / Potential Confounder	COLUMBUS trial data; Flatiron EHR	Indicates whether patients underwent chemotherapy or immunotherapy among those receiving prior systemic therapy
Number of LOTs after TT treatment initiation	Baseline Characteristic / Potential Confounder	COLUMBUS trial data; Flatiron EHR	Indicates the number of LOTs occurring after treatment initiation $(0, 1, \ge 2$, or Missing)
Number of organs involved	Baseline Characteristic	COLUMBUS trial data; Flatiron EHR	Indicates number of organs involved or sites of metastases at baseline (1, 2, or ≥3), with all patients having at least 1 site given diagnosis of metastatic disease. This data was collected and reported in COLUMBUS. In Flatiron EHR, it will be derived based on counting the number of distinct sites recorded as having metastases based on ICD codes.
Presence of lung metastases	Baseline Characteristic	COLUMBUS trial data; Flatiron EHR	Indicates whether patients had lung metastases. This data was collected and reported in COLUMBUS. In Flatiron EHR, it will be derived based on having ICD codes reflecting presence of lung or respiratory organ metastases (ICD-9: 197, 197.1; ICD-10: C78.01, C78.02, C78.1, C78.2, C78.30, C78.39).
Presence of liver metastases	Baseline Characteristic	COLUMBUS trial data; Flatiron EHR	Indicates whether patients had liver metastases. This data was collected and reported in COLUMBUS. In Flatiron EHR, it will be derived based on having ICD codes reflecting presence of liver metastases (ICD-9: 197.7; ICD-10: C78.7)
Presence of other metastases	Baseline Characteristic	COLUMBUS trial data; Flatiron EHR	Indicates whether patients had presence of other metastases (e.g., adrenal glands, bone, digestive tract/system, kidney, lymph nodes, reproductive organs, or unspecified sites). This data was collected and reported in COLUMBUS. In Flatiron EHR, it will be derived based on having ICD codes reflecting presence of other metastases (ICD-9: 196, 196.1, 196.2, 196.3, 196.5, 196.6, 196.8, 196.9, 197.4, 197.5, 197.6, 197.8, 198, 198.5, 198.7, 198.89; ICD-10: C77.0, C77.1, C77.2, C77.3, C77.4, C77.5, C77.8, C77.9, C78.4, C78.5, C78.6, C78.80, C78.89, C79.00, C79.01, C79.02, C79.11, C79.51, C79.52, C79.60, C79.61, C79.62, C79.70, C79.71, C79.72, C79.81, C79.89, C79.9)

